Title:

**Studying Hemostatic Effect of Axiostat Dressing on Radial Access After Percutaneous
Procedure (AHD)**

NCT02837744

Protocol ID: ABPL/002

Date: 31-Dec-2020

Protocol

Studying Hemostatic Effect of Axiostat® Dressing on Radial Access After Percutaneous Procedure (AHD)

Purpose

To evaluate Safety and Efficacy of Axiostat haemostatic dressing in terms of time to achieve immediate haemostasis, post application complication and comfort levels of patients.

Type of Study

Single Arm, Single Centre, Prospective

Study Population

Patients who undergo trans radial diagnostic or interventional cardiac procedures and who meet all eligibility criteria will be approached for participation in the study.

Inclusion Criteria

1. Age greater than or equal to 18 years.
2. Patient and/or patient's legal representative and/or impartial witness has/have been informed of the nature of the study and agrees to its provision and has provided written informed consent as approved by the Ethics Committee of the investigative site.
3. Iatrogenic puncture
4. Patient who want to undergo radial intervention.
5. All puncture size must be less than 2.5cm.

Exclusion Criteria

1. Prior diagnosis of disease or medical condition affecting the ability of blood to clot (e.g., hemophilia.).
2. Patients with known sensitivity to chitosan (shellfish) used in this study.
3. Patients who, in the opinion of the Investigator, may not complete the study for any reason, e.g. Patient requiring Immediate suturing.
4. Patient is currently participating in an investigational drug or dressing study that has not yet completed its primary endpoint interferes with procedure and assessments in this study.
5. Pregnant women.
6. Patients with hemorrhagic shock.
7. Patient having hemoglobin < 9 g/dl.

Primary Outcome

Time to achieve hemostasis by observing the time at which blood oozing through or from periphery of the dressing stops.

Secondary Outcomes

- (i) Number of patients with rebleeding will be counted
- (ii) Quantity of product used
- (iii) Skin Irritation and Hematoma formation
- (iv) Ease of use of Product
- (v) Patient Comfort Levels

Materials and Methods:

Study Material

Axiostat® - Size: 3.5 cm X 3.5 cm

Axiostat Chitosan Hemostatic dressing belongs to an advanced class of wound dressing that stops bleeding within few minutes of application by providing an active mechanical barrier.

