Investigators shall report all adverse events on the Adverse Event Report Form. All Serious Adverse Event (SAE) need to be reported to the sponsor within 24 hours after the investigator becomes aware of the event. SAE reporting will be done using the Event Reporting Form.

All adverse events need to be reported in the Adverse Event Report Form till patient discharge from hospital for the procedure, if any. Ethics Committee (EC) will be notified for any occurrence of SAE as required per local regulations. Sponsor will be responsible to notify any occurrence of SAE to competent authorities, if applicable

Sample Size

From available literature [1], with the assumption that Axiostat® will decrease time to haemostasis by 30%, minimum number of patients needed for study (with alpha 0.05 and power 0.8) was 15 patients. A total of 75 patients will recruited, with drop-out rate of 10%, ~ 67 patients will be included in the study

Statistical Analysis Plan

Pearson correlation analysis will be performed to check the co-relation between primary efficacy endpoint. Independent sample t-test will be performed to compare the mean of hemostasis time between independent categorical variables. A P-value of ≤ 0.05 will be considered to be significant. Secondary endpoint will be analyzed by descriptive statistics.

References:

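### No planned analysis gives an overall estimate of time to haemostasis or tests the 30% decrease on which the sample size rests

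*Combined protocol and SAP*

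**What the plan says.** All references are to the combined protocol and SAP.

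- **Purpose:** "To evaluate Safety and Efficacy of Axiostat haemostatic dressing in terms of time to achieve immediate haemostasis", along with complications and comfort.
- **Type of Study:** "Single Arm, Single Centre, Prospective". There is no concurrent control.
- **Primary Outcome:** "Time to achieve hemostasis by observing the time at which blood oozing through or from periphery of the dressing stops".
- **Sample Size:** the calculation is made "with the assumption that Axiostat® will decrease time to haemostasis by 30"%, and the "minimum number of patients needed for study (with alpha 0.05 and power 0.8) was 15 patients". The planned number is then set higher: "A total of 75 patients will recruited, with drop-out rate of 10%, ~ 67 patients will be included in the study". The 30% is attributed to one literature source, which the References section shows to be a comparative study in femoral access. No reference time, SD, sidedness or test is given.
- **Statistical Analysis Plan:** four sentences in all. The first is "Pearson correlation analysis will be performed to check the co-relation between primary efficacy endpoint". The second is "Independent sample t-test will be performed to compare the mean of hemostasis time between independent categorical variables". The third sets significance at P ≤ 0.05. The fourth provides descriptive statistics for the secondary endpoint.

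No section contains a historical control, a performance goal, a one-sample test, or a confidence interval for the primary endpoint.

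**The concern.** Alpha and power have meaning only in relation to a test. The sample size supposes that haemostasis time will be compared with something and found 30% shorter, but neither inferential sentence in the analysis plan makes such a comparison.

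The correlation sentence cannot be carried out as written, because a correlation needs two variables and only the primary endpoint is named. With one arm, the t-tests can only compare groups of patients who were all given the dressing. Descriptive reporting is assigned to the secondary endpoint, so the plan does not commit to an overall summary of the primary one.

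Followed to the letter, the plan yields p-values about differences between kinds of patient. It yields no single figure, with its uncertainty, for how long haemostasis takes with the dressing. If a reference time is chosen only after the data are seen, a comparison with it will carry little weight.

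**Working it through.** **1. The plan's own figures.** The allowance for drop-out reproduces: 75 × 0.9 = 67.5, given as about 67. The minimum of 15 can be neither confirmed nor refuted, because the documents give no SD, reference mean, sidedness or test. What can be done is to find the coefficient of variation (CV = SD divided by the reference mean) that would lead to 15 for a 30% decrease at 80% power. By the normal approximation, with k = 2.8016 two-sided and 2.4865 one-sided:

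| Reading of n = 15 | Formula for CV | Two-sided | One-sided |
|---|---|---|---|
| One sample against a fixed value | 0.30 × √15 / k | 0.41 | 0.47 |
| Two samples, 15 per arm | 0.30 × √7.5 / k | 0.29 | 0.33 |
| Two samples, 15 in total | 0.30 × √3.75 / k | 0.21 | 0.23 |

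The range is about 0.21 to 0.47. The exact t calculation gives 0.39 for the one-sample two-sided reading and 0.28 for 15 per arm two-sided.

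**2. What the planned p-values respond to.** Multiply every haemostasis time by a constant c > 0.

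- In the t-test, the difference in means and its standard error are both multiplied by c, so t is unchanged.
- In the Pearson correlation, the covariance and the SD of haemostasis time are both multiplied by c, so r is unchanged whatever the second variable proves to be.

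Every planned p-value is therefore the same whether all times are 30% shorter, unchanged or doubled. A simulation agrees. With 67 patients split 34 and 33, no true difference between the groups and 20,000 replicates per setting, the t-test rejected in 0.049, 0.052 and 0.051 of replicates when the true mean was 100%, 70% and 40% of the reference.

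**3. What 67 patients could support.** For the mean, the 95% CI half-width is t(0.975, 66)/√67 = 0.244 SD. That is 7.3% of the mean at CV 0.30, 14.6% at 0.60 and 24.4% at 1.0.

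For a one-sample two-sided t-test against a fixed reference time T0, 80% power at n = 67 needs a standardised difference of 0.347. The detectable reduction is 0.347 × CV:

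- CV 0.21: 0.347 × 0.21 = 0.073, about 7%
- CV 0.47: 0.347 × 0.47 = 0.163, about 16%
- CV 1.0: 0.347, about 35%

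Power for a 30% reduction with 67 patients is 0.98 at CV 0.60, 0.90 at 0.75, 0.79 at 0.87 and 0.68 at 1.0.

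The CVs are assumptions. The figures in this step are for the mean; the precision of a median depends on the shape of the distribution, about which the documents say nothing.

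**The case against.** The best defence is that the 30% appears once, as a sizing assumption. No hypothesis, success criterion or comparative objective is declared. The Purpose can be met in part by reporting the observed times in a single-arm study of a dressing that is already CE-certified and used within its approved application. This stands. A reader might infer that the trial cannot answer its own efficacy question, but the documents do not support that: the data could still be summarised, or compared with a reference fixed in advance. What remains is that the sizing assumption is not connected to any analysis and that no overall primary summary is planned.

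It can also be said that a t-test requires the mean in each category, so some information on speed would come out. That is right, and the invariance argument applies to the p-values only. But means in unnamed categories are not an overall estimate with a confidence interval.

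A reader might further infer that a significant subgroup result would be presented as proof of efficacy. Nothing in the plan links P ≤ 0.05 to an efficacy claim, so this is conjecture and the point does not rest on it.

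Finally, the cited study might be thought to supply the benchmark. None of its values is carried into the plan, and it concerns femoral access whereas this trial is radial, so using it would need justification.

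**Conclusion.** The point holds as a mismatch between the sample size and the analysis. The analyses named are the wrong ones for the stated purpose: none gives an overall estimate of time to haemostasis, none tests the assumed 30% decrease, and the power of 0.8 applies to no planned test. This follows from the wording and from scale invariance, and needs no assumption about variability.

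The documents do not show that 15 is wrong or that 67 is too few. Under the CVs that fit n = 15, about 67 patients would give 80% power against a fixed reference for reductions of about 7% to 16%. Only with a CV above roughly 0.87 would power for a 30% reduction fall below about 0.8. These figures assume a one-sample two-sided t-test and a CV that the documents do not state.

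**What to change.** Replace the first two sentences of the Statistical Analysis Plan with one primary analysis in all treated patients: the median time to haemostasis with its 95% CI as the single deciding summary, and the mean as supportive.

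Patients recorded as dressing failures after two applications should stay in the analysis as not having reached haemostasis with the dressing. Rank them as the longest times, do not drop them or treat them as ordinary censoring, and report their number. The supportive mean needs a stated rule for them too.

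Then choose one of two courses:

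- **(a)** State that the trial is descriptive, and remove the 30% and power statement as an efficacy hypothesis. This is the only option that the present documents support.
- **(b)** Write a justified radial-access reference time T0 into the protocol before any data are examined, and claim faster haemostasis only if the upper 95% limit lies below T0. Report the estimated percentage reduction with its CI.

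Under (b), do not require the upper limit to lie below 0.70 × T0. If the true reduction were exactly 30%, a two-sided 95% CI would meet that rule only about 2.5% of the time. For the mean at CV 0.386, 80% power would need a true reduction of about 30 + 0.347 × 38.6 = 43%.

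Label the correlation and t-tests exploratory and name their variables.

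No extra patients or measurements are needed. Option (a) costs wording and limits the conclusion to description. Option (b) also needs a radial benchmark from outside these documents.

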The dressing is approved in Europe (CE Certified) for the closure of arterial access sites and will be used in this study according to the approved application.

Screening Evaluation & Enrolment

Each potential subject who meets the protocol inclusion and exclusion criteria will be given a description of the study dressing, informed about the goals, risks-benefits and then invited to voluntarily participate in the study. Investigator will answer all the questions asked by patient and/or patient's representative. If a patient/patient's representative or impartial witness voluntarily agrees to participate in the study, he/she will read, understand, sign and date the informed consent form prior to the initiation of any study procedure. Each subject is free to withdraw from the study at any time during the study period.

Application of Axiostat

Inspect the puncture site to assess for inclusion in the study.

Make Sure to wear gloves

Open the dressing pack carefully (Axiostat tends to stick with blood on gloves)

- Remove the sheath and apply Axiostat along with the cotton gauze. Allow blood about 1 or 2 ml of blood to come in contact with Axiostat.
- Make sure Axiostat is placed directly above the puncture site.
- Apply pressure with fingers for about 5 minutes until dressing adheres to blood on puncture site and stays in position.
- Apply secondary dressing (as per Institutional care) such as Dynaplast Bandage. Do not remove or move Axiostat from position during this procedure and keep Axiostat in position for at least 30 minutes.
- If bleeding is persistent, then remove the first Axiostat and apply another Axiostat, on puncture bleeding site. Repeat the same procedure of treatment application.
- Failure to achieve haemostasis after two applications will be noted as dressing failure. In case of dressing failure, patient will be treated as per institutional standard of care.

Time, at which blood oozing through or from periphery of the dressing stops, will be considered as achieving haemostasis and will be noted as the efficacy endpoint.

Axiostat can be kept on site for 24 hours.

Removal of Axiostat: Axiostat must be removed by irrigating it with saline solution / water and gently lifting it off.

Patients will be followed up till discharge.

Training: Training will be rendered to four catheterization laboratory (cathlab) operators for application and direction of use of Axiostat as per study protocol.

Adverse Event Reporting

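### The SAP tests haemostasis time across unnamed, uncounted subgroups at P ≤ 0.05 each, with no multiplicity control, no exploratory label and no value for dressing failures

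*Combined protocol and SAP*

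**What the plan says.** The Type of Study section describes the trial as "Single Arm, Single Centre, Prospective", so the planned t-tests compare patient subgroups, not treatments. The Statistical Analysis Plan section is one short paragraph. On the primary endpoint it states: "Independent sample t-test will be performed to compare the mean of hemostasis time between independent categorical variables". The decision rule is: "A P-value of ≤ 0.05 will be considered to be significant". A Pearson correlation is also planned, but only one side of the correlation is named. For the rest: "Secondary endpoint will be analyzed by descriptive statistics".

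No categorical variable is listed, and no number of variables is given. There is no multiplicity rule, no multivariable model and no exploratory label.

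The Application of Axiostat section says that a patient in whom the second dressing also fails is recorded as a dressing failure and passes to institutional care. Neither that section nor the SAP gives such a patient a haemostasis time, a censoring rule or a rank.

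**The concern.** The plan sets a rule under which any categorical variable on the case report form may be tested, and each P ≤ 0.05 counts as a finding. No comparator test and no test of the assumed 30% reduction is specified, and the secondary endpoints are descriptive. Any significance claim the trial makes about haemostasis time must therefore come from this open family or from the incomplete Pearson analysis. A reader of the report could not tell how many variables were tried.

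Dressing failures are a separate problem. They are the worst outcomes on the primary endpoint, yet a mean needs a number for each patient. The analyst would have to drop them or invent a value. If failures are dropped and are more frequent in one subgroup, that subgroup looks better than it is.

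**Working it through.** **The plan's own figures.** The plan states: "A total of 75 patients will recruited, with drop-out rate of 10%, ~ 67 patients will be included in the study". This reproduces: 75 × (1 − 0.10) = 67.5. The minimum of 15 patients can be neither confirmed nor refuted, because no standard deviation (SD) is given. It follows from a coefficient of variation of about 0.41 in a two-sided one-sample calculation (n = (CV × (1.96 + 0.84) / 0.30)², with CV 0.41 giving 15 after rounding up), or of about 0.29 with 15 per group in a two-sample calculation. Neither calculation matches the subgroup t-tests the SAP plans.

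**Inputs.** The per-test threshold of 0.05 is from the SAP. The number of tests, k, is not in the documents, so a range is shown.

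**Chance of at least one false positive**, all nulls true, independent tests: 1 − 0.95^k.

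- k = 1: 5.0%
- k = 2: 1 − 0.9025 = 9.8%
- k = 3: 1 − 0.8574 = 14.3%
- k = 5: 1 − 0.7738 = 22.6%
- k = 10: 1 − 0.5987 = 40.1%
- k = 20: 1 − 0.3585 = 64.2%

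The expected number of false positives is 0.05k, which is 0.5 for ten tests.

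**Correlated variables.** Patient characteristics overlap, so independence overstates the figure. Simulation with 67 patients, lognormal times and binary factors with an assumed latent correlation of 0.3 to 0.6 (2,000 runs each) gave about 22% to 16% for k = 5 and 36% to 31% for k = 10. The chance is smaller, but still well above 5%.

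**Effect of adjusting instead.** With Bonferroni and k = 10 the threshold is 0.05/10 = 0.005, and the chance of any false positive is 1 − 0.995^10 = 4.9%. In a 33 v 34 split, the smallest difference detectable with 80% power rises from (1.960 + 0.842) × √(1/33 + 1/34) = 0.68 SD to (2.807 + 0.842) × √(1/33 + 1/34) = 0.89 SD. Adjusting many tests is therefore costly at this sample size.

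**Is each single t-test sound?** These checks were all simulated at n = 67, and every distribution, split, SD ratio and intra-operator correlation (ICC) is assumed.

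- *Skew.* Under lognormal, exponential and two-cluster shapes, with splits from 33/34 to 7/60, the pooled t-test had a type I error of about 4% to 5%. There was no inflation. The Welch form on raw times did inflate in unbalanced splits: about 6% to 12% at 13/54 and 8% to 19% at 7/60.
- *Unequal variance, 20 v 47.* If the smaller group has 1.5 to 3 times the SD, the pooled test's error is about 9% to 17%. If the larger group has it, the error is about 2% to under 1%. At 33 v 34 it stays between 5% and 6%.
- *Operator.* At an ICC of 0.05, a factor unrelated to operator gave about 5%, and a factor wholly determined by operator (two operators against two) about 14%.

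**The case against.** The strongest reply is that 0.05 is a per-test threshold and the SAP claims no family-wise rate. The study is single arm, subgroup comparisons do not test the dressing, and with one or two variables the rate is only 5% to 10%. Even with ten independent null tests, no false positive is the likelier result. Naming the variables and labelling the comparisons exploratory would then be enough.

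Much of this stands. The effect is confined to subgroup findings and depends on a count the documents do not give. What it does not answer is that the SAP calls each result significant without any label or limit, and specifies little else that could yield a significance claim.

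A reader might also infer stronger points, which the documents do not support:

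- *That false findings will occur.* This needs a number of tests that is not stated.
- *That skewed times inflate the error.* No distribution is given, and plausible skew does not inflate the pooled test.
- *That times are clustered by operator.* The Training paragraph says only: "Training will be rendered to four catheterization laboratory (cathlab) operators". It gives no operator effect, ICC or patients per operator, and inflation requires the tested factor to follow operator.
- *That the t-test's error is generally above 5%.* Unequal variance can push it either way, and the SAP does not say that the equal-variance form will be used.
- *That the test will be misapplied to factors with more than two levels.* No such factor is named.

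**Conclusion.** The point holds as a gap in error control and in the definition of the analysis. The chance of at least one false significant determinant is 14%, 23% or 40% for 3, 5 or 10 independent null tests, and about 16% to 22% for 5 or 31% to 36% for 10 if the variables are moderately correlated. These figures rest on an assumed number of tests and on all nulls being true. Separately, the lack of any value for dressing failures means that a comparison of means cannot include every treated patient as the plan is written. This follows from the text and needs no assumption beyond at least one failure occurring.

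Unequal variance and operator effects remain conditional concerns that rest on assumed group sizes, SD ratios and ICCs, and the conclusion does not depend on them. The description of haemostasis time in the whole group is not affected by the multiplicity problem. This is a cheap improvement and does not threaten the trial's main description.

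**What to change.** In the Statistical Analysis Plan section:

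1. Name at most one contrast to be tested at 0.05. Diagnostic against interventional procedure is one example, since the Study Population section already names both groups. The sponsor may choose another before seeing the data.
2. State one test for it: a Wilcoxon rank-sum test on time to haemostasis, with all dressing failures sharing the worst rank. This keeps failures in the analysis without inventing a time for them, and it does not depend on the shape of the times.
3. Report every other subgroup comparison, and the correlations, as estimates with 95% confidence intervals, labelled exploratory and with no significance claim. List the variables in advance and complete the Pearson sentence by naming what is correlated with haemostasis time.

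The cost is a few sentences of SAP text, with no change to sample size or patient care. The downside is that fewer results can be called significant.
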